7.2. Other Ethical Considerations

Recruitment will be performed by a consultant neurosurgeon experienced in performing pineal region surgery. There will be no therapeutic promises, coercion or inducement of any sort.

Date and Version No:

A minimum of personal data and no participant-identifiable data will be gathered.

The only interventions are questionnaires and most questions are expansions of existing nonstandardised symptom and lifestyle clinical interview caried in routine clinical practise.

8. DATA HANDLING AND RECORD KEEPING

All patient data will be anonymised. The participants will be identified by a study specific participant number. The information linking each number and the details of each participant will be stored securely in a separate file. All data will be identified by the participant number only. All data will be stored securely on Cambridge University Hospitals (CUH) NHS Trust computing clusters only. This is secure access and backed up automatically. No data will be stored on personal computers.

9. SPONSORSHIP, FINANCING AND INSURANCE

The study is jointly sponsored by the Cambridge University Hospitals NHS Foundation Trust.

All procedures will be done in NHS premises as part of the routine clinical care for patients.

Financing: No funding is required for this study as the amount of 'research-related' work is minimal and this work will be done on volunteer bases by the study participants and investigators.

10. POTENTIAL EXPANSIONS OF THE STUDY

This study may be expanded to a small number (one or two) of additional UK-based neurosurgical centres. Amendments to protocols and ethics application will be submitted as required prior to conducting any such potential expansions.

1. SYNOPSIS

Study Title	Assessment of changes in quality of life and symptoms over time in
	patients with symptomatic pineal cysts treated with surgery or
	conservatively - a prospective observational cohort study
	conservatively a prospective observational confer study
Internal ref. no.	
Study Participants	Patients with symptomatic pineal cysts (SPCs)
Planned Sample Size	40 surgically treated patients and all conservatively treated patients at
	the same period.
	As a result of Amendment 1, 21 consecutive patients who underwent
	an operation during the 5-year period prior to the commencement of
	the study (i.e. since 1st January 2016) and completed the required
	questionnaires and consented to participating in the study will be
	included in the total number of 40 surgically treated patients. These
	patients will be included in the total number of 40 surgically treated
	patients.
	The primary outcome will be assessed once 40 surgically treated
	patients reach 12-months follow up. Since all the data required to
	assess the primary outcome was collected as a part of clinical care and
	will be available if patients consent for this to be used in the study, it
	may only be necessary to recruit 19 patients since the commencement
	of the study in order to achieve the primary objective as well as
	secondary objectives 3.2.1. and 3.2.2. of the study.
	We will analyse and publish the result of the study with N=40. The cohort
	will consist of patients operated on before and after the commencement

	of the study. We will also evaluate the available data pertaining to the					
	rest of the secondary objectives (3.2.3, 3.2.4) and exploratory objectives					
	(3.3.1,3.3.2). These data will be less complete and results less					
	informative as a consequence of the Amendment, but the steering					
	committee believe this is a practically and ethically beneficial					
	compromise to mitigate the negative impact of the covid-19 pandemic					
Planned Study Period	Up to 5 years (2-year recruitment, 1 –year follow up, 2 more years for					
	long-term follow up)					
Primary Objective	Assessment of the impact of surgery on quality of life, specifically					
	patients' role functioning at one year after resection of symptomatic					
	pineal cyst.					
Secondary Objectives	1. Assessment of all aspects of quality of life as defined by the EORTC					
	QLQ-C30 questionnaire at 1 year and also at 2 and 3 years after surgery.					
	2. Assessment of symptoms at 1 year and also at 2 and 3 years after					
	surgery.					
	3. Assessment of all aspects of quality of life and symptoms in patients					
	who did not undergo surgery (= conservative management) at the time					
	of diagnosis and at 1, 2 and 3 years after joining the study; and					
	investigation the differences at baseline and follow up between those					
	treated surgically and conservatively.					
	4. Comparison of objective neuropsychological assessments before the					
	operation and at 1 year after surgery.					
	5. Development of a model to identify anatomical (based in MRI scans)					
	and clinical (symptoms) predictors of improvement of QoL after surgery					
	for SPC					
Study design	Prospective observational cohort study					

Date and Version No: 28/06/2021 Version 1.2

Interventions No interventions. This is an observational study.	
---	--

2. BACKGROUND AND RATIONALE

Pineal cysts (PCs) are benign, non-cancerous cysts arising from the pineal gland. While PCs are common (they can be identified on 2-4% of MRI scans(Golzarian et al., 1993)(Mamourian and Towfighi, 1986)(Nevins et al., 2016)), symptomatic pineal cysts (SPCs) are much rarer. While incidental PCs (i.e. discovered incidentally on a scan done for another reason) are thought to have no long-term consequences, patients with SPCs may suffer a number of chronic and acute symptoms, including headaches, vision and eye movement abnormalities, impairment of balance problems, speech and other cognitive problems, hydrocephalus, pineal apoplexy and even sudden death as a direct result of their pineal cyst (Nevins et al., 2016)(Koziarski, Podgórski and Zieliński, 2019)(Májovský, Netuka and Beneš, 2017)(Fedorko, Zweckberger and Unterberg, 2018)(Kalani et al., 2015)(Eide and Ringstad, 2017)(Choque-Velasquez et al., 2019)(El Damaty et al., 2019).

The exact incidence of SPCs is not known but, based on the numbers of contacts made with Pineal Cyst UK (PCUK) and the number of new patients we saw in the Eastern Region in 2019, we estimate that there are 200 new cases of SPC in the UK each year. The average age of patients with SPC is 35 years and the symptoms have major impact on patients' quality of life (QoL), including their role in family, work and society at large(Fedorko, Zweckberger and Unterberg, 2018).

[name], an Australian SPC patient and a patient group moderator, has shared with us a survey of people with SPCs (79%) and pineal tumours (21%) the group conducted in 2018([name], 2018). The most frequently reported symptoms were headaches, visual symptoms, fatigue, sleep problems, hearing and balance problems, feeling of being disconnected from the surroundings, speech, memory and other cognitive problems. Very similar lists of symptoms have also been reported in the medical literature(Májovský, Netuka and Beneš, 2017)(Májovský, Netuka and Beneš, 2018)(Májovský, Netuka and Beneš, 2016)(Koziarski, Podgórski and Zieliński, 2019)(El Damaty et al., 2019)(Kalani et al., 2015)(Fedorko, Zweckberger and Unterberg, 2018)(Choque-

feelings of helplessness, isolation and dejection. Often, several layers of symptoms can accumulate, making the task of identifying the true root cause very difficult.

It is therefore essential to learn more about the safety and efficacy of surgery in controlling patients' symptoms and its effect on patients' quality of life, and to determine the predictive value of symptoms, radiological findings and their combination on patients quality of life after surgery. We propose a prospective observational cohort study that will prospectively collect clinical and radiological data on all patients with SPCs, whether they chose surgically or non-surgical (conservative) management. This will provide higher level of evidence regarding the safety and efficacy of improving patients' QoL than the published retrospective studies, but will also provide valuable information for predicting such improvement based on prospectively and systematically collected clinical and radiological data. Ultimately, a randomised control trial of surgery versus conservative management is likely to be required to provide definitive evidence for the efficacy of surgery and this prospective study will serve as a pilot for planning of such an RTC.

Year	Journal	1 st author	Country	N	Symptom improvement*	Improvement in QoL
2015	J of Neurosurgery	Kalani	Australia	18	94%	NFI
2017	World Neurosurgery	Majovsky	Czech Republic	21	95%	NFI
2017	Acta Neurochirugica	Eide	Norway	15	100%	NFI
2019	Surgical Neurology International	Choque- Velasquez	Finland	60	100%	NFI
2019	Brit J Neurosurg	Koziarski	Poland	28	97%	NFI
2019	World Neurosurgery	El Dalmaty	Germany	43	95%	NFI
2019	J of Neurosurgery	Fedorko	Germany	12	100%	Yes
2019	Surg Neurol Internat	Choque- Velasquez	Finland	60	98%	NFI

Date and Version No:

Table 1. *Symptom improvement - % patients with symptoms improvement after surgery when compare to before surgery

NFI – not formally investigated, QoL – QoL

3. OBJECTIVES

3.1. PRIMARY OBJECTIVE

To assess the impact of surgery on quality of life, specifically patients' role functioning derived by the EORTC QLQ-C30 at one year after resection of symptomatic pineal cyst. Role functioning reflects activities in daily life, which is a higher-order outcome than symptoms, i.e. both symptoms and treatment have an impact on the level of functioning, a clear picture of the functioning of the patient. Role functioning was also the most relevant issue to patients seen in the clinic and the members of Pineal Cyst UK.

3.2. SECONDARY OBJECTIVES

3.2.1. Quality of Life – before and after surgery

We will determine the probability of improvement of overall QoL as well as each individual domain, as defined by the EORTC QLQ-C30 questionnaire (Appendix 1). This will be done by comparing pre-operative and post-operative assessments at 3, 12, 24 and 36 months following resection of SPC.

3.2.2. Symptoms – before and after surgery

We will determine the relative predictive values of individual symptoms and signs as well as their combinations in predicting improvement following resection of SPC. This will be done by comparing pre-operative and post-operative assessments at 3, 12, 24 and 36 months following resection of SPC.

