4.1. INCLUSION CRITERIA

- Age =/> 16 years
- Pineal cyst > 9mm in maximum diameter (Májovský et al., 2017)
- Symptom category B (total score ≥5) according to Eide and Ringstad(Eide and Ringstad, 2017) Figure 1_Eide symptoms
- Willingness and ability to comply with study specific procedures and completion of QoL and symptoms questionnaires.
- Written informed consent

Acta	Neurochir	2017	159:349	-361

Symptom	Severity	Score
Headache	No	0
	Minor-moderate	1
	Severe	2
Nausea/vomiting	No	0
	Yes	1
Dizziness	No	0
	Yes	1
Visual disturbances	No	0
	Yes	1
Episodic loss of consciousness	No	0
	Yes	1
Lethargy/fatigue	None-moderate	0
	Severe	1
Cognitive impairment	No	0
	Minor-moderate	1
	Severe	2
Transient neurological deficits	No	0
	Yes	1
Total score		0/10 - 10/10

Symptom category A (none-moderate), 0–4/10 scores; symptom category B (much-severe), 5–10/10 scores

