4.4.2. Secondary outcomes

The secondary outcomes are:

- 1. Change in all in items of QoL as defined by the EORTC QLQ-C30 questionnaire before and at 3, 12, 24 and 36 months following resection of SPC
- 2. Change of individual symptoms before and at 3, 12, 24 and 36 months following resection of SPC
- 3. Change in the results neuropsychological tests at 12 months following surgery when compared to baseline (before surgery)
- 4. Difference in severity of symptoms and QoL at baseline between patients who chose surgical and non-surgical treatment
- 5. Assessment of symptoms and QoL over (at diagnosis and 3, 12, 24 and 36 months later) in patients who chose not to undergo surgery
- 6. Development of a model to identify anatomical (based in MRI scans) and clinical (symptoms) predictors of improvement of QoL after surgery for SPC

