4.7.1. Questionnaires. - see above

4.8. DEFINITION OF END OF STUDY

The study will begin with at a given start date and will conclude after the last patient completes three-year questionnaire. (see also Flow Chart and Flow Table in the Appendix 7 and 8, respectively):

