5. INTERVENTIONS

The only interventions in this study are questionnaires that the patients will be asked to fill in. Please see section 4.6.

As a result of Amendment 1, the patients who had undergone surgery prior to the commencement of the study have already filled in some or all required questionnaires for the purpose of clinical management and will only be asked for a permission to use them for the purpose of this research study. In addition, they will be prospectively asked to fill in questionnaires that are due at the predefined future time points.

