6. SAFETY REPORTING

6.1 Safety data collection

This is an observational study where the only interventions are questionnaires and collection of clinical data. Nevertheless, this study presents an opportunity to systematically monitor surgical complications whose governance will fall into the realm of clinical rather than research governance. As such, we don't anticipate research-related events. Nevertheless, we will have system in place whereby any relevant events will feed into existing departmental governance structure.

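### Two of the eight entry-score symptoms, episodic loss of consciousness and transient neurological deficits, have no dedicated question on the forms shown, so the before/after change promised for individual symptoms rests on free text for these two; signs are promised but not defined

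*Supplement*

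**What the plan says.** Section 3.2.2 sets out to estimate the "relative predictive values of individual symptoms and signs as well as their combinations" for improvement after resection, and gives the method: "This will be done by comparing pre-operative and post-operative assessments at 3, 12, 24 and 36 months following resection of SPC". Section 4.4.2, item 2, lists the matching outcome as "Change of individual symptoms before and at 3, 12, 24 and 36 months following resection of SPC". Signs are not named there.

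Section 4.7 gives one line on assessment methods: "4.7.1. Questionnaires. - see above". Section 5 states that "The only interventions in this study are questionnaires that the patients will be asked to fill in". Section 6.1 is slightly wider: "the only interventions are questionnaires and collection of clinical data".

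Section 4.1 requires a total of at least 5 on an eight-symptom score running from 0 to 10. Two of the eight are "Episodic loss of consciousness" and "Transient neurological deficits", each scored 0 or 1.

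Under Amendment 1 (section 4), 21 patients operated on before the study started count among the 40 surgical patients. The same section says that with them 19 new patients may be enough for the primary objective and for objectives 3.2.1 and 3.2.2.

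**The concern.** To report change in a symptom, the study needs to ask about it before and after surgery. Both of these symptoms can help a patient qualify, yet none of the forms shown asks directly about either. If the forms are used as they stand, the study cannot report systematically whether these symptoms resolve, persist or appear after surgery.

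Free text does not repair this. A patient who had loss of consciousness at entry and does not write it down afterwards may have recovered, may have forgotten it, or may have used the three available lines for other complaints. The analyst cannot tell these apart, and reading blanks as absence would favour apparent resolution.

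Signs raise a related problem. They appear in an objective, but the plan gives no list of signs, no recording method and no corresponding outcome.

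**Working it through.** **The score.** Maximum points in the order of section 4.1: headache 2, nausea/vomiting 1, dizziness 1, visual disturbance 1, loss of consciousness 1, fatigue 1, cognition 2, transient deficits 1. The sum is 2+1+1+1+1+1+2+1 = 10, as the protocol states.

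**Item match against the forms shown.**

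| Entry symptom | Points | Pre-operative form | 3- and 12-month forms | QLQ-C30 |
|---|---|---|---|---|
| Headache | 0–2 | own section | own rating | – |
| Nausea/vomiting | 0–1 | – | – | items 14, 15 |
| Dizziness | 0–1 | own section | own rating | – |
| Visual disturbance | 0–1 | own section | own rating | – |
| Loss of consciousness | 0–1 | none | none | none |
| Fatigue | 0–1 | – | – | items 10, 12, 18 |
| Cognition | 0–2 | memory, concentration | memory, concentration | item 25 |
| Transient deficits | 0–1 | partial overlap: vision, speech, legs, balance | partial overlap: vision, speech, balance | none |

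Six of eight have a matching question and two do not. The free-text routes are an open question on other symptoms before surgery and, after it, up to three patient-named earlier symptoms plus a list of new problems. No form has a field for an examination finding.

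**Effect on the score.** The two items hold 2 of 10 points. Let S be the total of the other six items at follow-up (0 to 8), taken as known.

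- S ≤ 2: at most 2+2 = 4, so category A whatever the missing items are.
- S = 3: 3 to 5, because 3+2 = 5, so the category is undetermined.
- S = 4: 4 to 6, because 4+1 = 5, so the category is undetermined.
- S ≥ 5: category B whatever the missing items are.

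The category is lost only for S of 3 or 4, but the score itself is incomplete for everyone. The protocol gives no prevalence for either symptom, so the number of patients affected cannot be stated.

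**Who has a baseline value.** Screening (section 4.3) requires category B, so all eight items have to be considered for each prospectively screened patient. With 21 of 40 surgical patients from before the study, that leaves 40 − 21 = 19 (47.5%). For the 21 (52.5%), sections 4.5.1 and 5 name completed questionnaires as the source for past visits and do not mention an item-level entry score.

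**Sample size.** The calculation for the primary outcome is not involved. For completeness, the SD of the difference is √(42² + 18² − 2 × 0.5 × 42 × 18) = √1332 = 36.50, and a two-sided paired t-test at 5% with 90% power for 20 points needs 37 patients, as stated.

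**The case against.** The strongest reply is that questionnaires are not the only data source, whatever sections 4.7 and 5 suggest. Section 6.1 mentions clinical data, section 2 clinical and radiological data, section 3.2.4 objective neuropsychology before surgery and at 12 months, and section 3.3.1 routine MRI. This stands against the inference that no sign is ever recorded. What can be said is that no sign is itemised: sections 2 and 6.1 give neither items nor time points, and neuropsychology and MRI serve other objectives.

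A reader might also infer that the two symptoms cannot be analysed as predictors. The documents do not support that. Predictors are pre-operative values, and screening generates them for prospective patients. Whether they are kept singly is simply not stated.

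Nor are four of the eight symptoms missing: nausea/vomiting and fatigue are on the QLQ-C30. Transient deficits are partly reached through double vision, speech problems, loss of control of the legs and the time course of balance problems. That overlap is real, but it does not identify a transient neurological deficit as the entry score counts it, and it does nothing for loss of consciousness.

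Finally, the entry score is an eligibility rule. No objective or outcome promises to repeat it or to report movement between categories A and B, so its absence at follow-up breaks no promise. Neither symptom is on section 2's list of the most frequent complaints. Nor does the protocol support calling them the more serious ones: each scores 1, while headache and cognition score up to 2.

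**Conclusion.** The concern holds in a limited form. On the forms shown, two of eight entry symptoms have no dedicated before/after question, so the change promised in objective 3.2.2 and secondary outcome 2 is not measured systematically for them. The 0–10 entry score cannot be rebuilt from the forms after surgery. Signs are promised in 3.2.2 without a definition.

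This rests on the pre-operative, 3-month and 12-month forms and the QLQ-C30. The 24- and 36-month forms, any form specific to the conservative cohort, and the flow table are not shown. It would therefore go too far to say that these symptoms are unmeasured at every visit or in both cohorts.

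One secondary objective and one secondary outcome are affected. The primary outcome, role functioning at 12 months, is not.

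**What to change.** 1. Add two yes/no questions in present-state wording, one on loss of consciousness and one on transient neurological deficits, to the symptom form at baseline and every remaining visit in both cohorts. First confirm that the forms not shown lack them.
2. Store the screening entry score item by item, and say whether item-level scores exist for the 21 pre-study patients.
3. Optionally, repeat the entry score at follow-up as a descriptive analysis. It should be scored as at screening, because the post-operative study forms rate headache and cognition as better or worse rather than in the score's severity grades.
4. Delete the reference to signs from section 3.2.2, or name the signs to be taken from routine notes and the visits at which they are taken.

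No new questions on nausea/vomiting or fatigue are needed.

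The cost is a small form amendment, plus a short extraction sheet if signs are kept. Past visits of the 21 pre-study patients stay missing for these items, which should be stated when 3.2.2 is reported. Visits they still have due can carry the new questions, since section 5 already asks them to complete those.

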3.2.3. Quality of life and symptoms of patients treated conservatively

We will assess Quality of Life and Symptoms of patient who chose conservative management at enrolment and at 3, 12, 24 and 36 months following the diagnosis of SPC. These data will also serve to compare baseline Quality of Life and Symptoms between patients managed surgically and conservatively. We will explore the differences of outcomes of patients who

choose conservative and surgical treatments with adjusting confounding factors. This cohort will also give us an idea about changes in severity of symptoms and QoL over time.

3.2.4. Cognitive status and emotional wellbeing – before and after surgery

As with most other resective brain surgery, SPC patients undergo detailed objective neuropsychological assessments before and after surgery. For the sake of the study this will be done systematically, with a standard protocol and in predefined intervals, i.e. before and 12 months after surgery. (Appendices 1-3)

3.3. EXPLORATORY SECONDARY OBJECTIVES

3.3.1. MRI-based anatomical and physiological predictors of outcome after surgery

The mechanisms underlying clinical presentation in patients with SPCs is largely unknown. This prospective cohort study offers a unique opportunity to collect data that will help our understanding of the physiological bases of patients' symptoms. We will use MR imaging to understand aetiology of symptoms of in patients with SPCs and to predict improvement of symptoms following surgery. In addition to searching for biomarkers, the data will be used in this exploratory part of the study. We will use MR imaging acquired for routine clinical reasons to determine anatomical (size, deformation of the tectum, relationship with great veins, relationship of size and tecto-callosal distance etc) and physiological (flow through the aqueduct of Sylvius, the deep cerebral venous system) predictors of improvement following resection of SPCs by comparing pre- and post-resection data.

